6.4 Sample Size and Power

Sample size calculations are based on having at least 8 practices with a minimum of 5 clinicians per practice. Clinically important and conservative estimates of validated 12-month quit rates based on prior studies are 13.8% in the iEHR + Navigator group and 7% in the usual care control group. These estimates are based on the worst-case scenario from prior studies where all enrolled parents lost to follow-up were assumed to be smokers at 12-month follow-up. The effective sample size needed for the primary outcome accounts for clustering at the clinician and practice level (4 practices per arm x 5 clinicians per practice) with intra-class correlation of .014 calculated from our previous research. By enrolling approximately 100 parents in each practice (400 per arm), we will have 80% power for the primary outcome (iEHR + Navigator vs. usual care control). Effect sizes for outcomes other

than cessation will likely be much greater; the study will have adequate power to detect these differences, shown in our prior studies.

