2. Establish the incremental cost per quit of intervention. The healthcare system's perspective is central to establishing the interventions' disseminability and sustainability. As a secondary analysis, we will consider costs from a societal perspective to pave the way for future cost-utility analyses. We will calculate the incremental cost per quit of the iEHR+Navigator intervention relative to usual care, as we have done in prior studies: $(\text{Total cost at 12 months}_{\text{arm[i]}} - \text{Total costs}_{\text{arm[j]}}) / (\text{Total biochemically confirmed quits at 12 months}_{\text{arm[i]}} - \text{Total biochemically confirmed quits at 12 months}_{\text{arm[j]}})$. Development costs for iEHR will not be included in primary analyses as the iEHR will be fully developed and ready for dissemination by the time the intervention begins. Direct costs include iEHR set-up, customizing, implementing, and sustaining the systems changes that support service delivery and cessation, electronic tablets, and related clinician work. Direct costs further include: the CEASE intervention staff time to support the practice leader and the time clinicians and office staff take to learn and use the online module. Time use will be tracked by administrative records, direct observation by the RA, and surveys. For the iEHR+Navigator arm, we will create a log to note the types of CHN outreach efforts, time spent, and the type of services delivered to smoking parents. Personnel costs will reflect national average wages for each personnel type. We will use Monte Carlo simulation methods to develop confidence bounds on our cost-per-quit estimates. Following standard methods of economic evaluation in prior studies, we will also perform parameter-specific sensitivity analyses in which individual parameters are varied singly and in combination, through plausible ranges to assess the relative impact different elements of the program have on overall cost-effectiveness.

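### Monte Carlo bounds are put directly on the cost-per-quit ratio, with no rule for the case where the interval for incremental quits includes zero (about 20% of trials at the planned effect and power)

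*SAP*

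**What the plan says.** The SAP, under Secondary outcomes, item 2, sets out the estimand: "We will calculate the incremental cost per quit of the iEHR+Navigator intervention relative to usual care, as we have done in prior studies". The formula that follows is the difference between arms in total cost at 12 months, divided by the difference between arms in total biochemically confirmed quits.

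Uncertainty is covered in two sentences. One is "We will use Monte Carlo simulation methods to develop confidence bounds on our cost-per-quit estimates". The other adds that "we will also perform parameter-specific sensitivity analyses in which individual parameters are varied singly and in combination, through plausible ranges".

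The SAP does not say which inputs the simulation draws or how the bounds are formed from the draws. Neither document says what to report if the quit difference is small, negative or not statistically clear. Neither plans a cost-effectiveness plane, net benefit, an acceptability curve or a Fieller interval.

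The expected size and precision of the denominator come from Protocol 6.4. The assumed quit rates are "13.8% in the iEHR + Navigator group and 7% in the usual care control group", and "By enrolling approximately 100 parents in each practice (400 per arm), we will have 80% power for the primary outcome".

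**The concern.** A cost-per-quit ratio is ordered by value only while incremental quits keep the same sign. With a positive cost difference, a draw with slightly more quits gives a very large positive ratio, which is poor value. A draw with slightly fewer quits is worse still, because it costs more and achieves less, yet its ratio is large and negative. Sorting the draws puts this worst outcome at the low end, where genuine savings would also fall. The lower bound then looks too good. The upper bound is too low as well, because the worst draws have left the upper tail.

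Incremental cost per quit is a named secondary objective (Protocol 2.2 and 6.2), and the SAP ties the health-system cost perspective to whether the programme can be spread and sustained. A reader of the results could take a negative lower bound as a possible saving when it reflects draws in which the intervention is dominated.

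**Working it through.** **Inputs.** From Protocol 6.4: quit rates 0.138 and 0.07, 400 parents per arm, intra-class correlation 0.014, and 4 practices of 5 clinicians per arm (20 parents per clinician, 100 per practice). No inflation for dropout is needed, since the rates come from studies in which "all enrolled parents lost to follow-up were assumed to be smokers at 12-month follow-up". Assumed here: a two-sided 5% test, because 6.4 states no alpha.

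**1. Reproduce the stated power.** The design effect is 1 + (m − 1) × 0.014.
- Clinician level, m = 20: 1 + 19 × 0.014 = 1.266, so the effective n is 400 / 1.266 = 316 per arm and the power is 0.801. The stated 80% is reproduced.
- Practice level, m = 100: 1 + 99 × 0.014 = 2.386, so the effective n is 400 / 2.386 = 167.6 and the power is 0.53 to 0.54, depending on the variance formula.

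**2. The denominator.** Expected incremental quits are 400 × (0.138 − 0.07) = 27.2. The standard error in quits is 400 × √[(0.138 × 0.862 + 0.07 × 0.93) × DE / 400], where the bracketed sum is 0.184.
- Clinician level: SE = 9.65, expected z = 27.2 / 9.65 = 2.82.
- Practice level: SE = 13.25, expected z = 27.2 / 13.25 = 2.05.

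**3. How often the interval for incremental quits includes zero.** This happens when the observed z is below 1.96. The share of simulated quit differences at or below zero is then Φ(−z), which exceeds 2.5%, so a 2.5th percentile of the ratio falls among the negative draws.
- Planned effect, clinician level: 1 − 0.80 = 20% of trials.
- Planned effect, practice level: 1 − 0.537 = about 46% (47% with the other variance formula).
- Half the planned effect (10.4% vs 7%, assumed), clinician level: SE = 8.95, z = 13.6 / 8.95 = 1.52, power = Φ(1.52 − 1.96) = 0.33, so about 67%.

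A point estimate of incremental quits at or below zero is much rarer. At the planned effect it is Φ(−2.82) = 0.24%, or Φ(−2.05) = 2.0% with practice-level clustering.

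**4. What the percentile bounds look like.** The documents give no cost figure. Assumed: incremental cost $200,000, SD $20,000, with normal draws for cost and quits. Dollar values scale in proportion to the assumed cost.

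| Observed z | SE (quits) | Draws ≤ 0 | Point | 95% percentile bounds |
|---|---|---|---|---|
| 2.82 (planned effect) | 9.65 | 0.24% | $7,350 | about $4,100 to $23,300 |
| 1.5 | 9.65 | 6.7% | $13,800 | about −$90,000 to +$122,000 |
| 1.5 | 13.25 | 6.7% | $10,100 | about −$66,000 to +$89,000 |

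The z = 1.5 bounds move by about $1,000 between simulation runs.

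**5. Compare with what the data would support at z = 1.5, SE 9.65.** Incremental quits are 1.5 × 9.65 = 14.5, with 95% interval 14.5 ± 18.9, or −4.4 to 33.4. Holding cost at $200,000, the compatible values run from about $200,000 / 33.4 = $6,000 per quit upwards without limit, and on to no extra quits at extra cost. Neither −$90,000 nor +$122,000 describes that set.

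**6. If only costs are drawn.** At the same result the bounds are ($200,000 ± 1.96 × $20,000) / 14.475, or about $11,100 to $16,500. They are well behaved, but they ignore an interval for quits that includes zero.

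**The case against.** The strongest reply is that the SAP does not commit to a naive percentile method. It names Monte Carlo simulation, leaves the inputs and the construction of the bounds open, and refers to prior studies that cannot be seen here. This stands in part: the misordering follows only if quits are drawn and the ratios are sorted. It does not remove the point, because the alternative of drawing only costs leaves out the larger uncertainty (step 6). Either way the sentence needs completing.

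Second, a reader might infer that the stated power implies failure in at least one trial in five. The documents do not support that. The figure is about 20% at exactly the planned effect, under an alpha the protocol does not state, and a larger true effect lowers it. The 46% figure needs the intra-class correlation to act between practices, which 6.4 does not say. An observed z of 1.5 or below, as in the illustration, occurs in about Φ(1.5 − 2.82) = 9% of trials at the stated power.

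Third, a reader might infer that the bounds are meaningless in general. They are not: when the planned effect is observed they are finite, positive and interpretable.

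Fourth, no decision rule in either document depends on these bounds, and an interval from a large negative to a large positive value would itself suggest imprecision. That limits the consequence, but such an interval still misstates which direction is unfavourable.

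**Conclusion.** The concern holds in a conditional form. When the 95% interval for incremental quits includes zero, percentile bounds on the ratio are misordered and lose coverage if sampling error in quits is drawn. If it is not drawn, they omit the main uncertainty. The plan has no fallback for this case.

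At the planned effect and stated 80% power the condition arises in about 20% of trials. The share is larger with a smaller true effect or practice-level clustering (about 46%), and smaller with a larger effect. These shares rest on a two-sided 5% level and normal approximations. The dollar figures rest on an assumed cost and only illustrate the pattern; the sign problem does not depend on them while incremental cost is clearly positive.

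The documents do not show that a dominated result would be reported as a saving, only that nothing in the plan guards against that reading. The point should be addressed before analysis. It concerns a secondary outcome and leaves the primary comparison unchanged.

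**What to change.** Amend SAP Secondary outcomes, item 2, to say the following.

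- Costs and quits are both drawn, and the quit draws reflect clustering. With only four practices per arm, drawing from the fitted mixed model already planned for the primary outcome is likely to be steadier than resampling practices.
- The joint draws of incremental cost and incremental quits are shown on the cost-effectiveness plane, with incremental net benefit or an acceptability curve over a stated range of value per quit. Both stay defined whatever the sign of the quit difference.
- Bounds on the ratio are given only when the 95% interval for incremental quits excludes zero. Otherwise the two increments are reported with their own intervals.

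The cost is a few sentences, a little more analysis on the same simulations, and the need to state a range of values per quit, which the documents do not currently give. No new data are needed.
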